1. OBJECTIVES

1.1. Primary Objective

To establish that patients can be treated with 5-fraction SBRT to all sites of metastatic disease with a low (<16%) rate of severe (grade 4) toxicity.

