Concept and Rationale: Patients with metastatic renal cell carcinoma (RCC) have a poor prognosis with median survival between 6-15 months, as few patients have a lasting response to cytokine therapy or targeted agent therapy. However, not all patients present with widely metastatic disease. There may be a select group of patients with “oligometastatic” disease—a limited number of metastatic lesions that can be treated with curative intent using aggressive local and systemic therapy. Randomized studies suggest a benefit of cytoreductive surgery in the setting of cytokine therapy, and retrospective series suggest an improvement in survival with metastasectomy. These studies argue that aggressive local therapy to all known sites of disease can yield benefit in the properly selected patient.

However, not all lesions are amenable to surgical resection, and surgery can be associated with significant morbidity. Stereotactic Body Radiotherapy (SBRT) is a method of treatment which directs ablative doses of radiotherapy to the target lesion while limiting radiation to surrounding structures. There is an increasing body of evidence supporting a role for SBRT in oligometastatic cancers throughout the body. A prior Phase I trial at the University of Chicago suggested that a 3-fraction regimen is tolerable in oligometastatic cancer. However, this study included a heterogeneous cohort of patients with multiple primary malignancy types; only 13% of the patients in the trial had RCC. Furthermore, variable radiation doses were prescribed to different sites, complicating the applicability of findings to the clinical setting. Conclusions are therefore more difficult to make regarding the tolerability of SBRT in RCC.

We hypothesize that 5-fraction SBRT with a more uniform dose approach (by having a preferred SBRT dose that is similar for all sites of involvement) in the management of oligometastatic RCC is feasible, not associated with excess toxicity, and can be safely delivered prior to systemic therapy. Information gathered from this study will contribute towards the development of a larger, phase II Chicago consortium study.

Primary Objective: To establish that patients can be treated with 5-fraction SBRT to all sites of metastatic disease with a low (<16%) rate of severe (grade 4) toxicity.

Secondary Objectives:

1. To determine the toxicity profile of SBRT.

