2. To determine the feasibility of delivering 5-fraction SBRT per protocol based on proposed normal tissue constraints in a variety of organ sites. (i.e., the ability to treat >80% of enrolled patients according to protocol guidelines).
3. To describe treated lesion control (LeC), progression free survival (PFS), and patterns of failure.
4. To determine the feasibility of accrual and adequacy of eligibility criteria by defining the proportion of eligible cases of metastatic RCC presented at the weekly multidisciplinary genitourinary conference at the University of Chicago Medical Center.
5. To make a preliminary evaluation regarding potential biomarkers in patient serum which may be assessed in a follow-up study (e.g. genetic or immunologic biomarkers).

Study Design: This is a single-armed pilot study to estimate the rate of CTCAE v4.0 grade ≥ 4 RT-related toxicity of 5-fraction SBRT in patients with oligometastatic RCC. Eligible patients must have histologically or cytologically diagnosed RCC with 1-5 sites of metastases, including up to 3 brain metastases. Patients may present with metastatic disease, or have previously treated primary disease with metastatic recurrence. All sites of metastasis must be ≤ 6 cm, and patients with recurrent/unresected primary tumors are eligible as long as said tumor is ≤ 10 cm and there is a plan to treat the primary tumor with a local therapy. Patients may not have had any oncologic therapy within 1 month prior to enrollment, no prior history of bevacizumab, and any brain metastases must be addressed with surgery and/or radiotherapy prior to enrollment. Patients will be treated with SBRT (preferred dose 50 Gy/5 fractions) to all radiographic sites of gross disease, including the primary if it can not be addressed with non-radiotherapeutic local therapy. Patients can thereafter begin off-protocol systemic therapy per medical oncology discretion, but any therapy will occur no earlier than 2 weeks after completion of RT.

The first 10 patients enrolled on the study will be considered the "initial cohort." If ≥ 3 of these patients have a CTCAE v4.0 grade ≥ 4 RT-related toxicity, enrollment will be discontinued and the trial stopped, otherwise 5 additional patients will be accrued. Study investigators will determine whether treatment related toxicities are RT-related or non-RT-related.

Statistical Methods:

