Definition of primary outcome/endpoint: RT-related grade ≥ 4 toxicity will be determined on a case-by-case basis by the study group, taking into consideration the region treated with SBRT, timing of the toxicity, and the nature of the toxicity. Toxicities will be graded as per CTCAE v4.0 criteria.

Definition of secondary outcomes/endpoints: LeC will be defined as absence of clinical or radiographic progression per RECIST criteria. PFS will be defined as progression in the treated lesion, organ in which the treated lesion is present, distant failure, or death from any cause.

Analytic plan for primary objective: Rates of RT-related grade ≥ 4 toxicity will be recorded, time to RT-related grade ≥ 4 toxicity will be recorded, and freedom from RT-related grade ≥ 4 toxicity will be determined using the Kaplan-Meier method.

Analytic plan for secondary objectives: LeC and PFS will be estimated at 1 year using the Kaplan-Meier method.

Sample size justification: A sample size of 25 patients will be needed to assess the safety and appropriateness of this method, identify the optimal candidates, and optimal SBRT fractionation/dose for different clinical scenarios.

TABLE OF CONTENTS

	Page
SCHEMA	i
1. OBJECTIVES	1
1.1 Primary Objectives	1
1.2 Secondary Objectives	1
2. BACKGROUND	1
2.1 Metastatic Renal Cell Carcinoma	1
2.2 Oligometastasis	1
2.3 Stereotactic Body Radiotherapy in Oligometastasis	2
2.4 Rationale for current study	3
2.4.1 Rationale for Secondary Objectives	4
3. PATIENT SELECTION	4
3.1 Eligibility Criteria	4
3.2 Exclusion Criteria	5
3.3 Inclusion of Women and Minorities	6
4. REGISTRATION PROCEDURES	6
4.1 Patient Recruitment	6
4.2 Patient Renumeration	6
5. TREATMENT PLAN	6
5.1 Study Design	6
5.2 Definition of Grade ≥ 4 RT-related Toxicity	6
5.3 General Concomitant Medication and Supportive Care Guidelines	7
5.4 Duration of Therapy	7
5.5 Duration of Follow Up	7
5.6 Criteria for Removal from Study	7
6. RADIATION THERAPY	7
6.1 Simulation	7
6.2 Premedications	8
6.3 Target Volumes	8
6.4 Treatment Planning	8
6.5 Dose Specifications	8
6.6 Critical Structures	9
6.7 RT Treatment	13
6.8 Radiotherapy Adverse Events	13
7. RISKS AND BENEFITS	13
7.1 Radiotherapy Adverse Events	13
8. Adverse Event Reporting	15
9. Data Safety Monitoring	16
10. STUDY CALENDAR	16
11. MEASUREMENT OF EFFECT	17
11.1 Antitumor Effect and Endpoints	17
11.2 Dosimetric description of delivery of Radiotherapy	18
12. STATISTICAL CONSIDERATIONS	19
12.1 Study Design/Endpoints	19

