2.4 Rationale for current study

The above evidence suggests a role for aggressive local treatment of metastatic lesions in RCC. We hypothesize that SBRT can be safely and effectively delivered in patients with oligometastatic RCC. Results will inform the development of a larger, multicentric trial.

This study will evaluate a 5-fraction regimen in patients who have a histology diagnosis of metastatic RCC with 5 or fewer sites of disease. All organs of involvement will receive 5 fractions with a preferred dose of 50 Gy in 5 fractions. This pilot study will evaluate the ideal candidates for this approach, the likely accrual and accrual rate of a phase II study, and the optimal dosimetric and dose/fractionation considerations in pursuing this approach. In addition, this study will allow for the collection of data to possibly refine eligibility and treatment

delivery for future studies, and help determine sample size calculations for the next generation trials. Subsequent testable hypotheses could include randomized comparisons of SBRT +/- concurrent molecularly targeted systemic therapy, observation +/- SBRT, or systemic therapy +/- SBRT.

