5. TREATMENT PLAN

5.1 Study Design

This is a pilot study of the use of SBRT to all sites of disease for patients with oligometastatic RCC. Patients may receive off-protocol systemic therapy per medical oncologist discretion no earlier than 4 weeks after starting SBRT. While there are no restrictions on systemic therapy following SBRT, caution is advised on the use of bevacizumab given prior case reports demonstrating the possibility of heightened toxicity when this agent is used in the setting of SBRT. Limited or symptomatic recurrences can also be treated with radiation therapy (either SBRT or conventional therapy) at the clinician's discretion.

Enrollment will proceed according to a sequential toxicity monitoring schema to test the null hypothesis of a $\pi_0=5\%$ grade 4 toxicity rate against an upper acceptable boundary of a $\pi_1=20\%$ grade 4 toxicity rate. Trial enrollment will be halted if there are two grade 4 events within the first 2 patients, if there are three events within the first 14 patients, or if there are four events within the first 25 patients. The treatment will be considered successful if there are less than four events in 25 evaluable patients (<16%).

Treatment will be administered on an outpatient basis. The details of planning and administration of radiotherapy are discussed in detail in section 6. Reported adverse events and potential risks for SBRT are described in Section 8. Appropriate dose modifications for SBRT are described in Section 6. No investigational or commercial agents or therapies other than those described below may be administered with the intent to treat the patient's malignancy.

The pilot study will be considered successful if 25 patients are accrued, with less than 4 having Grade 4+ toxicity events after SBRT.

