12. STATISTICAL CONSIDERATIONS

12.1 Study Design/Endpoints

This is a pilot study of the use of 5-fraction SBRT for oligometastatic RCC. Patients enrolled in the study will be treated with SBRT to all sites of disease. Enrollment will proceed according to a sequential toxicity monitoring schema [69] to test the null hypothesis of a $\pi_0=5\%$ grade 4 toxicity rate against an upper acceptable boundary of a $\pi_1=20\%$ grade 4 toxicity rate. Trial enrollment will be halted if there are two grade 4 events within the first 2 patients, if there are three events within the first 14 patients, or if there are four events within the first 25 patients. The treatment will be considered successful if there are less than four events in 25 patients, i.e., $<16\%$ observed toxicities. This design has approximately 80% power (78.8%) to declare the treatment too toxic if the true grade 4 toxicity rate is $\pi_1=20\%$.

Patients will be followed for a total of one year after completion of the trial per protocol. Patients may be treated with off-protocol systemic therapy no earlier than 2 weeks after completion of RT. The primary endpoint is the rate of grade 4 RT-related toxicity with this treatment approach. Secondary endpoints include determining the toxicity profile of 5-fraction SBRT, determining the feasibility of 5-fraction SBRT based on normal tissue dosimetric constraints based on the organ site of involvement, describing the LeC, PFS, and patterns of failure of this approach, as well as to explore the feasibility of accrual and the adequacy of the eligibility criteria of this approach.

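### The primary objective claims to establish a grade 4 toxicity rate below 16%, but 16% is only the observed cut-off of 4 in 25; a true 16% rate passes 38% of the time and no interval is planned

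*Combined protocol and SAP*

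**What the plan says.** The primary objective in section 1.1 is "To establish that patients can be treated with 5-fraction SBRT to all sites of metastatic disease with a low (<16%) rate"; the events meant are those of grade 4. The synopsis uses the same wording.

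The design sections define 16% differently. Section 5.1 states: "The treatment will be considered successful if there are less than four events in 25 evaluable patients (<16"%). Section 12.1 repeats the rule ("The treatment will be considered successful if there are less than four events in 25 patients") and describes the 16% as a rate of observed toxicities. The true rates that the design contrasts are 5% (null) and 20% (upper boundary). Enrollment halts at two events in the first 2 patients, three in the first 14, or four in the first 25. The only operating characteristic given is at 20%: "This design has approximately 80% power (78.8%) to declare the treatment too toxic" at that rate. Nothing is stated for a true rate of 16%, and no type I error is given.

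The Study Design paragraph of the synopsis puts the aim in other terms: "This is a single-armed pilot study to estimate the rate of CTCAE v4.0 grade ≥ 4 RT-related toxicity". For the analysis, the synopsis says that rates and times to event will be recorded and that "freedom from RT-related grade ≥ 4 toxicity will be determined using the Kaplan-Meier method". Section 12.4 names the rate and says who attributes toxicity to radiotherapy. Neither place, nor any other, specifies a confidence interval or upper limit for the rate.

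**The concern.** A cut-off on an observed proportion in 25 patients is not a bound on the true rate. The objective drops the qualifier *observed*, which section 12.1 carries, and uses the verb *establish*. Followed as written, a trial with 3 events in 25 meets the success rule and would be reported as having established a rate below 16%.

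The claim would be carried forward. Section 2.4 says the results are to inform a larger multicentre trial and "help determine sample size calculations for the next generation trials". The endpoint is severe toxicity, where overstating safety is the costly direction of error. Because no interval is planned, the report as specified would not show how far above 16% the true rate could lie.

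**Working it through.** **Inputs.** Boundary: stop at 2 events in the first 2 patients, 3 in the first 14, 4 in the first 25 (sections 5.1 and 12.1). Contrasted rates: 5% and 20% (same sections). Stated power: 78.8% at 20% (section 12.1). Cut-off: 4/25 = 16%.

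**Step 1: pass probability.** A trial passes if it has at most 2 events in the first 14 patients, not both of the first two patients with events, and at most 3 events in all 25. With true rate p and j events in the first 14,

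P(pass) = Σ over j = 0, 1, 2 of w_j × P(Bin(11, p) ≤ 3 − j),

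where w_0 = (1−p)^14, w_1 = 14p(1−p)^13 and w_2 = 90p²(1−p)^12. The 90 is the 91 ways to place two events in 14 patients, less the one way that stops the trial at patient 2. Checking after every patient or only at patients 2, 14 and 25 gives the same result.

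**Step 2: reproduce the stated power (p = 0.20).**
0.0440 × 0.8389 + 0.1539 × 0.6174 + 0.2474 × 0.3221 = 0.0369 + 0.0950 + 0.0797 = 0.2116.
P(stop) = 1 − 0.2116 = 0.7884, which matches the stated 78.8%.

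**Step 3: the null rate (p = 0.05).**
0.4877 × 0.9984 + 0.3593 × 0.9848 + 0.1216 × 0.8981 = 0.4869 + 0.3539 + 0.1092 = 0.9500.
The type I error, which the documents do not state, is 5.0%.

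**Step 4: the rate named in the objective (p = 0.16).**
0.0871 × 0.9154 + 0.2322 × 0.7479 + 0.2843 × 0.4547 = 0.0797 + 0.1737 + 0.1293 = 0.3827.
A true rate of exactly 16% passes 38.3% of the time. The final count alone, P(Bin(25, 0.16) ≤ 3), gives 41.6%. The true rate must reach about 24.2% before the full boundary passes it only 10% of the time, and about 27.6% for 5%.

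**Step 5: what each passing result can exclude.** Clopper-Pearson limits at n = 25. For x events the upper limit solves P(Bin(25, p) ≤ x) = α and the lower limit solves P(Bin(25, p) ≥ x) = α, with α = 0.025 for the two-sided 95% interval.

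| Events | Observed | Two-sided 95% | One-sided 95% upper | One-sided 90% upper |
|---|---|---|---|---|
| 0 | 0% | 0% to 13.7% | 11.3% | 8.8% |
| 1 | 4% | 0.1% to 20.4% | 17.6% | 14.7% |
| 2 | 8% | 1.0% to 26.0% | 23.1% | 19.9% |
| 3 | 12% | 2.5% to 31.2% | 28.2% | 24.8% |

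The documents set no confidence level. For 2/25 and 3/25 the upper limit exceeds 16% at all three levels shown, and at the two-sided 95% level it exceeds the design's own 20%. At one-sided 95% only 0/25 excludes 16%.

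**Step 6: allowance for sequential stopping.** Rank passes by event count and treat every stopped trial as more toxic. For 3/25 the upper limit then solves P(pass) = 0.025, giving 30.7%. The lower limit solves P(pass with 3 events, or stop) = 0.025, giving 2.5%. The adjustment changes little.

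**The case against.** The strongest reply is that the documents, read as a whole, already treat 16% as an observed go/no-go cut-off. Section 12.1 says so, sections 5.1 and 12.1 name the contrasted rates, and the synopsis uses the word *estimate*. On that reading the fault is one verb in two places. This explains the design, but the objective still carries the claim, and it is the objective against which the trial will be reported.

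Secondly, the rule was built for 20%, not 16%, and its error at 20% is disclosed. Any rate between 5% and 20% must pass with intermediate probability. That stands: 38.3% is not a defect of the boundary. It is evidence only that passing cannot establish a rate below 16%.

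Thirdly, some passing results are better than 2/25 and 3/25. At a true 5%, P(0 or 1 event) = 0.2774 + 0.3650 = 0.6424, so these results make up 0.6424/0.9500 = 67.6% of passes. A result of 0/25 does exclude 16%, and 1/25 does so at one-sided 90%. This also stands, but the success rule makes no distinction between these results and 3/25.

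Fourthly, the plan's silence does not bar an interval in the report, and a reader could compute one from the count. For a primary endpoint in a study meant to estimate a rate, the interval should still be specified in advance.

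Finally, a binomial interval needs a defined toxicity window and complete ascertainment, and section 5.2 mentions both a 90-day acute period and late events through one year. The plan's own count of fewer than 4 in 25 has the same need.

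**Conclusion.** The concern holds. The stopping boundary works as described and its power reproduces. The primary objective attributes to it a property it lacks: passing does not establish a true rate below 16%, since a true 16% passes 38.3% of the time and a true 20% passes 21.2% of the time. The largest passing count, 3/25, is compatible with a true rate of about 31%. No interval is planned that would show this.

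The calculations assume independent patients with a common toxicity rate, 25 evaluable patients, and the boundary in sections 5.1 and 12.1. The Study Design paragraph of the synopsis carries a different rule (at least 3 of the first 10 stops the trial, otherwise 5 more patients). That is a separate inconsistency to be reconciled; the 16% and the 78.8% belong to the 25-patient rule. The correction should be made, but it does not affect the conduct of the trial.

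**What to change.** 1. In section 1.1 and the synopsis, reword the objective: to estimate the rate of RT-related grade ≥ 4 toxicity and to screen out excessive toxicity (20% against 5%). This agrees with the synopsis Study Design paragraph.
2. In section 12.1, state that fewer than 4 events in 25 is a go/no-go rule on the observed rate. It would help, but is optional, to add the pass probabilities under the full boundary (38.3% at a true 16%, 21.2% at 20%) and the type I error of 5.0%.
3. In section 12.4, specify that the observed proportion will be reported with an exact 95% interval, either Clopper-Pearson or adjusted for the sequential stopping, alongside the Kaplan-Meier estimate planned in the synopsis. State the toxicity window to which the proportion refers.

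Leave the stopping and success rules unchanged, and add no second success criterion based on the upper limit. The cost is wording in three places and one interval, with no extra patients. The safety statement becomes less favourable: a passing 3/25 would be reported with an upper limit near 31%.

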1.2. Secondary Objectives

- 1.2.1 To determine the toxicity profile of SBRT.
- 1.2.2 To determine the feasibility of delivering 5-fraction SBRT based on proposed normal tissue constraints in a variety of organ sites. (i.e., the ability to treat >80% of enrolled patients according to protocol guidelines).
- 1.2.3 To describe treated lesion control (LeC), progression free survival (PFS), and patterns of failure.
- 1.2.4 To determine the feasibility of accrual and adequacy of eligibility criteria by defining the proportion of eligible cases of metastatic RCC presented at the weekly multidisciplinary genitourinary conference at the University of Chicago Medical Center.
- 1.2.5 To make a preliminary evaluation regarding potential biomarkers in patient serum which may be endpoints in a follow-up study (e.g. genetic or immunologic biomarkers).

2. BACKGROUND

2.1 Metastatic Renal Cell Carcinoma

Between 20-33% of patients with renal cell carcinoma (RCC) present with metastatic disease, and of patients with initially limited disease who undergo radical nephrectomy, approximately 25% will ultimately develop metastases [1, 2]. Most patients receive systemic therapy with cytokine therapy or molecularly targeted agents blocking the Vascular Endothelial Growth Factor (VEGF) pathway or mammalian target of rapamycin (MTOR). Despite these interventions, the response rate to systemic therapy is low, with 5-20% responding to cytokine agents and approximately 30-50% to small molecule receptor tyrosine-kinase VEGF inhibitors such as sunitinib and pazopanib [3-8]. Responses are generally of short duration and the median overall survival is typically between 6-15 months [8].

2.2 Oligometastasis

Not all patients with cancer present with widely metastatic disease, and there may be a select group of patients with a more indolent disease course. A select cohort of patients develops a limited number of metastatic lesions, and can potentially be treated with curative intent using aggressive local and systemic therapy [9, 10]. Hellman and Weichselbaum described the existence of an intermediate state in the development of metastatic disease described as oligometastasis [11] – a state where a patient may have a malignancy limited to only a few sites and regions, suggesting an underlying biology not yet capable of widespread metastasis.

The benefit of aggressive resection of metastatic tumors in patients with a limited number and sites of disease has been shown in various malignancies. In patients with metastatic colorectal cancer to the liver, there appears to be a benefit in survival for patients with favorable clinical factors who undergo resection of a limited number of liver metastases, and this approach can produce 5 year overall survival rates between 25-60% [12-16]. Patients with limited pulmonary metastases may have a similar benefit [17]. Similarly, patients with pulmonary metastases from soft tissue sarcoma may have 5 year overall survival rates of approximately 25% when they undergo resection of lung metastases [18-22].

For patients with metastatic RCC, there has been increasing use of cytoreductive nephrectomy prior to systemic therapy. Two randomized studies comparing immediate Interferon-alpha to initial cytoreductive nephrectomy followed by Interferon-alpha showed a benefit in time to progression and median survival in patients who underwent maximal cytoreduction of the primary tumor followed by adjuvant interferon alpha therapy [23, 24]. For patients treated with molecularly targeted agents, a multicenter retrospective series of 314 patients undergoing anti-VEGF therapy showed cytoreductive nephrectomy prior to systemic therapy improved overall survival (19.8 months vs. 9.4 months) [25]. An analysis of patients on a prospective open label, expanded access trial of sunitinib revealed that patients who had nephrectomy prior to sunitinib had a 9.8 month PFS, compared to 6 months for those who did not [26]. The Phase III CARMENA trial is currently assessing the role of cytoreductive nephrectomy prior to sunitinib therapy, and the SURTIME trial is assessing the appropriate timing of surgery in relationship to sunitinib therapy [27, 28].

In addition to resection of the primary tumor, many advocate removal of metastatic lesions in patients with a limited number of lesions of RCC. A retrospective study of 278 patients with metastatic RCC from Memorial Sloan-Kettering Cancer Center showed that patients who underwent surgical resection of metastatic lesions had an improved 5 year overall survival (44% vs. 11%) [29]. Additionally, the survival of patients after their second or third resection was not significantly lower. Eggener et al. reviewed 129 patients with recurrent and metastatic renal cell carcinoma. 34% of patients underwent metastasectomy, which was associated with a survival benefit [30]. Alt et al. reviewed 125 patients who underwent metastasectomy compared to 762 patients who did not. Complete metastasectomy was associated with improved cause-specific survival (median 4.8 vs. 1.3 years, $p < 0.001$). The benefit was present for both synchronous or asynchronous multiple metastases [31]. These data suggest that in a select group of patients, local eradication of metastatic lesions and unresected primary tumors may have a benefit in the survival of patients with metastatic RCC.

